## 5.5 Standardized questionnaires

Several standardized questionnaires will be administered to patients enrolled in the NORIG trial. Questionnaires will be administered at baseline (prior to randomization) and during follow-up at specified intervals (see Appendix 9.2 for the data collection schedule). The purpose of the

questionnaires is to obtain important information regarding gastroparesis symptoms, side effects, and health-related quality of life.

**Patient Assessment of Upper Gastrointestinal Disorders-Symptoms (PAGI-SYM).** A validated 20 question questionnaire that quantifies symptoms of gastroparesis, dyspepsia, and gastroesophageal reflux disease on a 0 to 5 scale for each symptom^21. The PAGI-SYM includes the 9 question Gastroparesis Cardinal Symptom Index (GCSI) - a validated symptom questionnaire that assesses the symptoms of gastroparesis. The GCSI is based on three subscales (postprandial fullness/early satiety, nausea/vomiting, and bloating). For this study, the total GCSI score, representing the sum of symptom scores of the 9 GCSI symptoms will be used.

**Gastrointestinal Symptom Rating Scale (GSRs)**. A clinical rating scale for gastrointestinal symptoms in patients with irritable bowel syndrome and peptic ulcer disease.

**Beck Depression Inventory**, Second Edition (BDI - II). The BDI-II is a commonly used, reliable 21-item self-report measure designed to assess for depression.

**State Trait Anxiety Inventory**. The STAI is a 40-item self-report measure designed to assess both situational and characterological anxiety. This measure provides two subscale scores (State and Trait) and has been shown to exhibit good reliability and internal consistency.

**Patient Health Questionnaire (PHQ-15)**. The PHQ-15 is a brief, self-report measure of somatization. This test has good internal consistency and reliability.

**Brief Pain Inventory.** (BPI). Developed in 1989 by [name] for rapid assessment of the severity and impact of pain in cancer patients. The BPI has since been translated into more than two dozen languages, and is widely used in both research and clinical settings.

**SF-36 Health Survey (SF-36)**. The SF-36 is a 36-item, self-report measure designed to assess quality of life in patients. This measure also provides two summary scores (physical and mental health) and eight scale scores. It is reliable and internally consistent.

**Gastroparesis symptoms/side effect profile:** The baseline and follow-up medical histories will inquire about symptoms that may be attributed as side effects of nortriptyline. These symptoms include drowsiness, fatigue, dizziness, seizures, sleep disturbance, palpitations, blurred vision, dry mouth, skin rash, and urinary retention. The symptom profile will include 2 questions:

The global overall relief of symptom question which requests a yes/no answer, asks, "During the past 7 days, have you had adequate relief of your stomach symptoms?"

The clinical global patient impression (CGPI) question helps quantify overall relief of symptoms. This question asks, "Please consider how you felt this past week in regard to your stomach symptoms, in particular your overall well-being and stomach symptoms. Compared to the way you usually felt before entering the study, how would you rate your relief of symptoms during the past week?"

3	2	1	0	-1	-2	-3
Completely Better	Considerably Better	Somewhat Better	Unchanged	Somewhat Worse	Considerably Worse	Very Considerably Worse

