#### Study duration – per patient

- Up to 16 weeks of screening prior to randomization, including a 6 week washout period for other tricyclic antidepressants (TCAs) or monoamine oxidase inhibitors (MAOI).
- 15 weeks of treatment starting at randomization
- Tapering off study drug by one capsule a week from 15 to 17 weeks after randomization
- One week with no study drug from 17 to 18 weeks after randomization

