#### 4.3 Exclusion criteria

Patients who satisfy any of the following exclusion criteria will be ineligible for randomization in the trial:

1. Normal gastric emptying confirmed with scintigraphy
2. Diabetic gastroparesis or post-surgical gastroparesis including fundoplication
3. Another active disorder which could explain symptoms in the opinion of the investigator
4. History of significant cardiac arrhythmias and/or prolonged QTc
5. History of seizures
6. Use of narcotics (including fentanyl patches) more than 3 days per week
7. Use of tricyclic antidepressants for refractory symptoms of gastroparesis within 6 weeks prior to randomization
8. Use of strongly anticholinergic medications
9. Use of calcium channel blockers
10. Use of erythromycin
11. Clear history of failed trial of nortriptyline use for gastroparetic symptoms
12. Symptoms of primary depression or suicidal ideation
13. Contraindications to nortriptyline:
  - a) hypersensitivity or allergy to any tricyclic antidepressant
  - b) concomitant therapy with a monoamine oxidase inhibitor (MAOI)
  - c) recent myocardial infarction
  - d) glaucoma
14. Pregnancy or nursing
15. Any other condition, which in the opinion of the investigator would impede compliance or hinder the completion of the study
16. Use of a G tube, J tube, or a central catheter for nutrition
17. Use of a gastric electrical stimulator
18. Failure to give informed consent

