As part of the screening process for the NORIG trial, the gastroparesis patient must have a standardized 4 hour scintigraphic evaluation of gastric emptying using a low fat Egg Beaters meal that is available for review by the study physician as outlined in the Standard Operating Procedures, Part I, section 6.3. This may be repeated as part of standard of care for diagnosis or follow-up as determined by the clinical center investigator during screening. The standard of care gastric emptying scintigraphy may have been obtained at any time within 2 years prior to the registration date. Patients must also have a negative upper endoscopy within the last 2 years, to rule out other potential causes of symptoms such as mechanical obstruction, inflammatory or other structural lesions of the GI tract or non-gastrointestinal causes. Recording of screening data on trial forms may not start until the patient has signed the NORIG trial consent statement. Screening and baseline data collection procedures will include questionnaires, physical examination, various laboratory tests, clinical procedures on patients and review of the patient's medical chart. Data abstracted from a patient's chart may include laboratory, endoscopy, scintigraphy and radiology test results. Prior therapy for gastroparesis will be reviewed, and patients will be asked to stop specific treatments such as tricyclic antidepressants, monoamine oxidase inhibitors, strongly anticholinergic medications, calcium channel blockers, and erythromycin. Narcotic pain medication including fentanyl patches and other rescue medications such as propoxyphene or propoxyphene with acetaminophen may not be used more than 3 days per week.

All participants who sign the consent statement will be registered in the trial database. Each participant who starts screening will be accounted for at the end of screening, as either a screening success (randomization) or a screening failure. A screening failure is defined as a participant who signed the consent form and was registered in the NORIG trial data system, but is found to be ineligible prior to randomization; screening failures include patients who meet medical eligibility criteria but change their mind and do not consent to randomization into the trial. The reason for screening failure will be recorded on the randomization form and keyed in the trial database.

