Screening and baseline data collection procedures will be conducted over two clinic visits completed on separate calendar days. The goal of the first screening visit is to obtain consent and start recording screening data regarding the trial's inclusion and exclusion criteria on NORIG data forms; the goal of the second screening visit is to complete collection of baseline data on patients who appear to be eligible. This separation of procedures between two visits is somewhat arbitrary and is provided as a guideline. Screening procedures and data collection can be organized as appropriate at each clinical center. The procedures completed during screening include:

- **Screening visit 1:** The patient should be in a fasting state (no food or drink after midnight the night before) for this visit. The patient will sign the consent at or prior to screening visit 1 and will undergo a history and physical examination to identify other illness and contraindications for participation such as use of narcotics for pain more than 3 days per week (including fentanyl patches), use of calcium channel blockers, use of erythromycin, use of medications that are strongly anticholinergic, hypersensitivity or allergy to any tricyclic antidepressant drug, concomitant therapy with a monoamine oxidase inhibitor (MAOI), recent myocardial infarction or glaucoma. The baseline medical history form will have a section to establish a baseline symptom profile for each participant and to document non-specific symptoms that may be attributed as side effects to study drug after randomization. The patient will be asked to respond to the clinical global patient impression (CGPI). Patients will complete the following questionnaires:

- Gastrointestinal Symptom Rating Scale (GSRS)
- Health-related quality of life questionnaire (SF-36)
- Beck Depression Inventory (BDI-II)
- Patient Assessment of Upper Gastrointestinal Disorders Symptom Severity (PAGI-SYM)
- State Trait Anxiety Inventory (STAI)
- Brief Pain Inventory (BPI)
- Patient Health Questionnaire (PHQ-15)

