Anthropometric assessments (body weight [kg], body height [m], body mass index [BMI], waist circumference [cm], hip circumference [cm], vital signs (systolic and diastolic blood pressure, heart rate, respiratory rate, body temperature); and general physical findings will be collected and recorded. Patients will have an ECG performed at this visit. Laboratory test results that need to be recorded from chart review or obtained as part of screening visit 1 include: complete blood count (CBC): white blood cells, red blood cells, hemoglobin, platelets; a metabolic panel: sodium, potassium, chloride, carbon dioxide, calcium, magnesium, blood urea nitrogen (BUN), creatinine; a hepatic panel: albumin, total protein, alkaline phosphatase, alkaline aminotransferase (ALT), aspartate aminotransferase (AST), bilirubin; and thyroid stimulating hormone (TSH).

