## 9.2 Data collection schedule

Assessment/Procedure	Screening Visits			Follow-up visits Weeks from randomization					
	s1	s2	rz	3	6	9	12	15	18
Consent	X	.	.	.	.	.	.	.	.
Gastric emptying scintigraphy review	X	.	.	.	.	.	.	.	.
Upper endoscopy review	X	.	.	.	.	.	.	.	.
Baseline medical history	X	.	.	.	.	.	.	.	.
PAGI-SYM questionnaire	X	.	.	X	X	X	X	X	X
GSRS questionnaire	X	.	.	X	X	X	X	X	X
SF-36 QOL questionnaire	X	.	.	.	.	X	.	X	.
Beck Depression Inventory-II	X	.	.	X	X	X	X	X	X
State Trait Anxiety Inventory	X	.	.	.	.	X	.	X	.
Brief Pain Inventory	X	.	.	.	.	X	.	X	.
PHQ-15 questionnaire	X	.	.	.	.	X	.	X	.
Electrocardiogram (ECG)	X	.	.	.	.	X	X	.	.
Physical exam	X	.	X	.	.	X	X	X	.
Satiety test with electrogastrography (EGG)	.	X	.	.	.	.	X	.	.
Study drug dispensed	.	.	X	X	X	X	X	.	.
Review of study drug adherence	.	.	.	X	X	X	X	X	X
Follow-up medical history including review of adverse events	.	.	.	X	X	X	X	X	X
Labs	.	.	.	.	.	.	.	.	.
CBC, metabolic and hepatic panel	X	.	.	.	.	.	X	.	.
TSH	X	.	.	.	.	.	.	.	.
Plasma banking	.	X	.	.	.	.	X	X	.
DNA banking	.	X	.	.	.	.	.	.	.
Pregnancy test	X	.	X	.	.	X	X	X	.

**Physical exam:** includes measurement of weight, height, waist and hip circumferences, vital signs (temperature, heart rate, blood pressure) general physical findings

**CBC:** Complete blood count: white blood cell count, red blood cell count, hemoglobin, hematocrit, platelet count

**Metabolic panel:** sodium, potassium, chloride, carbon dioxide, glucose, calcium, magnesium, blood urea nitrogen (BUN), creatinine.

**Hepatic Panel:** albumin, total protein, bilirubin, alkaline phosphatase, alkaline aminotransferase (ALT), aspartate aminotransferase (AST)

**TSH:** Thyroid Stimulating Hormone

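### The baseline side-effect profile is scheduled only at screening visit 1, possibly before a tricyclic washout, so for some patients it is an unreliable reference for attributing later symptoms to study drug

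*Protocol*

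**What the plan says.** Section 5.5 describes the side-effect profile: "The baseline and follow-up medical histories will inquire about symptoms that may be attributed as side effects of nortriptyline". It lists ten symptoms, among them drowsiness, dizziness, palpitations, blurred vision, dry mouth and urinary retention. Section 5.2, under screening visit 1, gives the purpose of the baseline part of the form: to set a symptom profile for each participant and "to document non-specific symptoms that may be attributed as side effects to study drug after randomization".

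In the schedule in 9.2, the row "Baseline medical history" is marked at s1 and nowhere else. The follow-up version is marked at weeks 3 to 18. Section 5.3 lists re-affirmed consent, vital signs and a pregnancy test at the randomization visit, and no symptom profile.

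On prior drugs, the synopsis gives the screening length as "Up to 16 weeks of screening prior to randomization, including a 6 week washout period for other tricyclic antidepressants (TCAs) or monoamine oxidase inhibitors (MAOI"). Section 4.3 excludes "Use of tricyclic antidepressants for refractory symptoms of gastroparesis within 6 weeks prior to randomization". In section 5.2, as part of screening, "patients will be asked to stop specific treatments such as tricyclic antidepressants, monoamine oxidase inhibitors, strongly anticholinergic medications" and others. Section 4.4 repeats the 6-week limits but adds that the agents it names may not be used during screening at all.

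**The concern.** A pre-treatment symptom record is useful for attribution only if it shows the patient as he or she is just before the first dose. Here it may be taken months earlier, while the patient is still on a drug of the same class as the study drug. Section 3.4 itself names dry mouth, dizziness and insomnia as common with tricyclics. Someone with a dry mouth from an earlier tricyclic at s1, who stops it and is free of the symptom at randomization, will still carry dry mouth on the baseline form. If it returns on study drug, the form suggests that it was there before.

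Section 1 makes the frequency of side effects under nortriptyline and placebo a study objective. What is at stake is reliable attribution in individual patients and, if new symptoms are counted against the s1 form, part of the difference between arms. The primary outcome is not involved in this point.

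**Working it through.** **Timing.** Inputs: screening of at most 16 weeks with the washout inside it (synopsis), and a tricyclic-free window of 6 weeks counted back from randomization (4.3). If s1 falls S weeks before randomization, tricyclic use can continue after s1 for at most S − 6 weeks:

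- S = 8: 8 − 6 = 2 weeks
- S = 12: 12 − 6 = 6 weeks
- S = 16: 16 − 6 = 10 weeks

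For any S above 6, the symptom record can therefore be made on a tricyclic and the washout can still be completed in time.

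**The passages side by side.**

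| Place | Tricyclic use at s1 |
|---|---|
| Synopsis, study duration | possible: washout lies within screening |
| 4.3, item 7 | possible: window counts back from randomization |
| 5.2 | possible: patients are asked to stop during screening |
| 4.4 | not possible: no use during screening |

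Three places allow it and one does not. The exposure depends on which one the centers follow.

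**Effect on the comparison of arms.** The protocol gives neither the share of patients on these drugs at s1 nor any side-effect rates, so the size cannot be derived from it. The following only shows direction and range, and every input is an assumption. Let a symptom be present in a share b of patients off drug, and in a share t on a tricyclic, whether the old one or nortriptyline. Let f be the share on a tricyclic at s1, equal in both arms by randomization. The true excess is t − b. The chance that a patient without the off-drug symptom reacts is s = (t − b)/(1 − b).

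If only symptoms absent at s1 are counted, the detected excess is:

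- same patients react to both drugs: (1 − f)(t − b)
- reactions independent: (1 − f)(t − b) + f(t − b)(1 − s)

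With b = 10% and t = 30%, the true excess is 20 points and s = 0.20/0.90 = 0.222:

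| f | Same patients | Independent |
|---|---|---|
| 5% | 19 | 19.8 |
| 10% | 18 | 19.6 |
| 20% | 16 | 19.1 |
| 30% | 14 | 18.7 |

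For example, at f = 30%: 0.70 × 20 = 14, and 14 + 0.30 × 20 × 0.778 = 18.7. With b = 20%, t = 50% and f = 30%, a true 30 points becomes 21 to 26.6.

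If nothing is subtracted and follow-up rates are compared directly, the result is t − b = 20 points at every f. Dilution thus needs both patients on such a drug at s1 and a counting rule that uses the s1 form.

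**The case against.** The strongest reply is that the protocol never says what is done with a symptom present at baseline. Section 5.11 has adverse events recorded whatever their presumed cause and has rates compared by treatment group. The symptom profile is taken at every follow-up visit, so on-treatment frequencies can be compared without the s1 form. Rules for treatment-emergent events commonly belong in the analysis plan, which is not at hand. This stands. A reader might infer that study-drug effects will be logged as pre-existing and the side-effect difference biased toward zero, but the protocol does not support that as a fact.

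Second, the side-effect outcome defined in 6.2 is side effects that require stopping medication, which hardly depends on the s1 form. That also stands, though section 1 states the wider objective.

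Third, section 5.2 calls the division between s1 and s2 a guideline that centers may rearrange, and the synopsis describes the randomization visit as including a final pre-treatment interview. Some centers may therefore already collect the symptoms after washout. But this permits a later record without requiring one, and practice could differ between centers.

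Fourth, section 4.4 read literally removes the exposure. It cannot be read alone, because the synopsis and 5.2 describe stopping these drugs within screening.

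A reader might extend the point to the screening ECG, which is also at s1. The QTc concern values in 5.7 are absolute, and no outcome is defined as change from the screening ECG, so the documents show no comparable consequence there.

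**Conclusion.** The point holds in a limited form. As scheduled, the only required baseline symptom profile can precede the end of tricyclic use by up to 10 weeks. For patients who stop a tricyclic or strongly anticholinergic drug after s1, it is an unreliable reference for its own stated purpose. Section 4.4 conflicts with the synopsis, 4.3 and 5.2 on whether such patients exist.

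Dilution of the between-arm difference in new side effects is conditional on s1 symptoms being treated as pre-existing. Its size is unknown: it depends on the share of patients exposed at s1, the side-effect rates, and how far the same patients react to both drugs. None of these is in the protocol. No loss of power can be claimed, since the protocol plans no powered test of a side effect. The case for change rests on a weak reference that is nearly free to repair.

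**What to change.** 1. Repeat the side-effect/symptom section of the medical history at the randomization visit, before the first dose: one mark under rz in 9.2 and one line in 5.3.
2. State that this record is the baseline for side-effect attribution. The s1 record stays as screening information.
3. Reconcile section 4.4 with the synopsis, 4.3 and 5.2 on use of the listed drugs during screening. Which rule should apply is for the investigators; this review takes no position on it.

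The cost is about ten short questions and a few minutes at a visit that already takes place, plus a small amendment. Sample size, dosing and the primary analysis are unchanged.

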### 5.6 Specimen repository

Biological specimens will be collected and stored for use as approved by the Steering Committee of the GpCRC (see Appendix 9.3 for whole blood draw schedule). Specimens to be stored include plasma and DNA. Blood will be collected at a screening visit and at follow-up visits (weeks 12 and 15) for plasma banking. The blood will be drawn in the morning during the study visit after the subject took the study medication the night before and is still fasting. The blood will be separated into plasma and will be divided into 0.5 mL aliquots. Plasma aliquots will be kept in a freezer at -70 degrees C and will be sent to the NIDDK Biosample Repository for banking. The plasma will be analyzed for nortriptyline levels at the end of the study. Nortriptyline levels will be determined using a Nortriptyline Immunoassay (Syrax Co., Palo Alto, CA) similar to that performed in the functional bowel disorder study by Drossman.

For each NORIG participant that consents to DNA banking, blood will be collected at a screening visit and will be sent to the NIDDK Genetics Repository. DNA will be extracted and will be stored at -20 degrees C for analyses of CYP2D6 polymorphisms.

### 5.7 Safety issues

Safety issues can be divided into (a) safety concerns relating to nortriptyline, (b) safety concerns related to study procedures, and (c) concerns related to patient privacy. The following paragraphs discuss the important potential adverse events and the proposed safeguards to minimize the risks involved.

#### **Safety concerns related to nortriptyline:**

Study participants will receive nortriptyline or placebo. Nortriptyline is a tricyclic antidepressant (TCA). Tricyclic antidepressants act to inhibit the reuptake of the neurotransmitters norepinephrine and serotonin, leading to an increase in their effects. Contraindications to nortriptyline include: a) hypersensitivity or allergy to any tricyclic antidepressant drug, b) concomitant therapy with a monoamine oxidase inhibitor, c) recent myocardial infarction, and d) glaucoma. The dose (10-75 mg) of nortriptyline in this study is on the lower end of the conventional antidepressant dose (50-150 mg) approved to treat depression. Patients with cardiovascular disease should be given nortriptyline only under close supervision due to increased risk of myocardial infarction, arrhythmia and stroke. Arrhythmias may develop especially in patients with hyperthyroidism or those receiving thyroid hormone replacement medication. Patients with a history of seizures will be excluded from the study because nortriptyline is known to lower the convulsive threshold. Concurrent administration of cimetidine with nortriptyline can produce

clinically significant increases in the plasma concentrations of nortriptyline.

Study participants will have an electrocardiogram (ECG) during screening and at follow-up visits 9 and 12 weeks after randomization to monitor for any signs of study-drug related toxicity. In addition, a complete blood count (CBC), a metabolic panel including sodium, potassium, chloride, carbon dioxide, calcium, magnesium, blood urea nitrogen (BUN), creatinine, and a hepatic panel including albumin, total protein, alkaline phosphatase, alkaline aminotransferase (ALT), aspartate aminotransferase (AST), and bilirubin will be performed at the week 12 visit. The following treatment interruption or termination rules will be followed:

- If hypokalemia (potassium  $<3.5$  mEq/L) or hypomagnesia (magnesium  $<1.5$  mEq/L) is present at the week 12 visit, study participants will be given oral supplementation and electrolyte measures will be repeated within a week. If the electrolyte imbalance has not been remedied with oral supplementation as indicated by a serum potassium of  $<3.0$  mEq/L and serum magnesium of less than 1.0 mEq/L, the study drug will be interrupted or terminated with tapering, as needed. The participant will continue with 15 week and 18 week follow-up visits as scheduled.
- If significant elevations ( $>2$  times upper limit or normal) occur in alkaline phosphatase, alkaline aminotransferase (ALT), or aspartate aminotransferase (AST) at the week 12 visit, these enzymes will be repeated within a week. If any of these enzyme elevations persist above 3 times the upper limit of normal, the study drug will be interrupted or terminated with tapering, as needed. The participant will continue with 15 week and 18 week follow-up visits as scheduled.
- If thrombocytopenia ( $<100,000$  cells per  $\mu$ L) is present at the week 12 visit, the study drug will be interrupted or terminated with tapering, as needed. The participant will continue with 15 week and 18 week follow-up visits as scheduled.

In general, side effects to nortriptyline are fewer than other TCAs since it does not have significant anticholinergic effects, however, side effects can still occur and can include: drowsiness, sedation, fatigue, dizziness, seizures, palpitations, blurred vision, dry mouth, constipation, and skin rash. A standardized management plan for the most common side effects as well as the more serious side effects are outlined below:

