**Exclusion criteria**

- Normal gastric emptying confirmed with scintigraphy
- Diabetic gastroparesis or post-surgical gastroparesis including fundoplication
- Another active disorder which could explain symptoms in the opinion of the investigator
- History of significant cardiac arrhythmias and/or prolonged QTc
- History of seizures
- Use of narcotics more than 3 days per week
- Use of tricyclic antidepressants for refractory symptoms of gastroparesis within 6 weeks prior to randomization
- Use of strongly anticholinergic medications
- Use of calcium channel blockers
- Use of erythromycin
- Clear history of failed trial of nortriptyline use for gastroparetic symptoms
- Symptoms of primary depression or suicidal ideation
- Contraindications to nortriptyline:

- a) hypersensitivity or allergy to any tricyclic antidepressant drug
- b) concomitant therapy with a monoamine oxidase inhibitor (MAOI)
- c) recent myocardial infarction
- d) glaucoma
- Pregnancy or nursing
- Any other condition, which in the opinion of the investigator would impede compliance or hinder completion of the study
- Use of a G tube, J tube, or a central catheter for nutrition
- Use of a gastric electrical stimulator
- Failure to give informed consent

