#### 4.4 Run-in period

Patients must not have used any tricyclic antidepressants for refractory symptoms of gastroparesis within 6 weeks prior to randomization. Patients must not have used a monoamine oxidase inhibitor (MAOI) for the 6 weeks prior to randomization. Patients must not have used a narcotic analgesic for abdominal pain, strongly anticholinergic drugs, calcium channel blockers, or erythromycin on a daily basis for the 6 weeks prior to randomization. These agents are not to be used during screening nor for the duration of the trial. Patients will be interviewed in a detailed fashion at screening, randomization, and at every follow-up study visit to document the absence of such use.

Patients will be allowed to continue on prescription gastroparesis medications as well as any over-the-counter medications or dietary supplements. If using a selective serotonin reuptake inhibitor (SSRI), the patient must have been on a stable dose in the 3 months prior to randomization.

---

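### Section 5.7 warns that cimetidine raises nortriptyline levels, but no instruction follows and none of the five medication lists restricts the drug

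*Protocol*

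**What the plan says.** Section 5.7, under the safety concerns for nortriptyline, states the interaction in one sentence: "Concurrent administration of cimetidine with nortriptyline can produce" "clinically significant increases in the plasma concentrations of nortriptyline". The next paragraph turns to ECG and laboratory monitoring. Cimetidine is not mentioned anywhere else.

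The drugs that sites must act on are listed in five places:

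- the synopsis exclusions, for example "Use of strongly anticholinergic medications";
- section 4.3, which opens with "Patients who satisfy any of the following exclusion criteria will be ineligible for randomization in the trial";
- section 4.4, which says of its listed drugs: "These agents are not to be used during screening nor for the duration of the trial";
- the section 5.2 list of treatments that patients are asked to stop;
- the section 5.2 check at screening visit 1.

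Section 4.4 then gives a general permission: "Patients will be allowed to continue on prescription gastroparesis medications as well as any over-the-counter medications or dietary supplements". The only condition attached there is a stable dose for patients on an SSRI.

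**The concern.** A protocol that calls an interaction clinically significant should tell the site what to do about it. Here the warning has no consequence, and the operative text leans the other way, since the over-the-counter permission in section 4.4 makes no exception for drugs that interact with the study drug.

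What is at stake is patient safety. Variable exposure to nortriptyline is accepted by design: section 2.7 says that CYP2D6 variants may call for 28-180% of the usual dose, and doses are set by tolerance, not by genotype. Cimetidine is a different case, because the extra exposure can be avoided and the protocol has already identified its source.

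**Working it through.** No formula applies. The check is a comparison of the warning with each place that could turn it into an action.

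**The five lists**

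| Place | Drug classes barred, stopped or limited | Cimetidine |
|---|---|---|
| Synopsis exclusions | 6: narcotics, tricyclics, strong anticholinergics, calcium channel blockers, erythromycin, MAOIs | no |
| Section 4.3 (items 6-10 and 13b) | the same 6 | no |
| Section 4.4 | the same 6 | no |
| Section 5.2, stop list | 5 to stop, with narcotics limited to 3 days per week | no |
| Section 5.2, screening visit 1 | 5 (tricyclics appear only as an allergy) | no |

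The count is 0 of 5.

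**Neighbouring cautions in section 5.7**

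Seizure history leads to exclusion. MAOI use is named as a contraindication and is excluded in section 4.3. For cardiac disease the text says: "Patients with cardiovascular disease should be given nortriptyline only under close supervision". The cimetidine sentence has nothing of this kind.

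**Other text that might close the gap**

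- Both section 5.2 lists are introduced as examples. An investigator may stop cimetidine on that basis but need not.
- Exclusion 15 in section 4.3 concerns conditions that threaten compliance or completion, not drug interactions.
- The medication review in section 3.5 is aimed at drugs that worsen dysmotility.
- The section 4.4 interview takes place "at every follow-up study visit to document the absence of such use". That refers to the listed agents, so cimetidine started during the trial is outside its stated scope.

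None of these requires a site to act.

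**Timing of the general safeguards**

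Section 5.7 and Appendix 9.2 schedule ECGs at screening, week 9 and week 12. Under section 3.3 the patient has taken 10 mg (weeks 0-3), 25 mg (weeks 3-6) and 50 mg (weeks 6-9) before the first on-treatment ECG. Side effects that are noticed but tolerated lead to continued escalation. Section 5.6 has plasma nortriptyline assayed only at the end of the study, so a raised level cannot guide dosing.

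**The case against.** The strongest reply is that nothing here is a false statement. Section 5.7 names four contraindications, and all four are carried into section 4.3. Cimetidine is given as a caution, and leaving a caution short of an exclusion is a clinical choice. It is also not the only caution without its own rule: the sentence on hyperthyroidism and thyroid hormone replacement has none either.

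The safety net is also fuller than the scheduled ECGs alone:

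- palpitations trigger an ECG at any dose (sections 3.4 and 5.7);
- patients are told to call in with a rapid heart beat, chest pain or orthostatic hypotension;
- QTc prolongation stops the drug;
- the week 9 ECG is reviewed before the 75 mg step;
- the dose range is at the lower end of the antidepressant range.

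Finally, the five lists overlap heavily, so 0 of 5 is largely one omission repeated. The standards-of-care procedures (SOP IV) are cited but not available, and the protocol does not say whether cimetidine is sold over the counter.

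These points limit the weight of the concern but do not answer it. Each safeguard in the list except the low dose range works only once exposure has risen, and QTc prolongation need not cause symptoms. The thyroid sentence is a parallel gap, not a reason to leave this one; TSH is at least measured at screening. An instruction in SOP IV cannot be ruled out, but the protocol's own eligibility and medication lists should still agree with its own warning.

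**Conclusion.** The concern holds, as an inexpensive improvement worth considering. The protocol flags an avoidable interaction as clinically significant, attaches no instruction, names the drug in 0 of 5 medication lists, and permits over-the-counter medication without exception.

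Confidence is high on what the text says and omits. No figure can be given for the harm, because the protocol states neither the size of the interaction nor how often these patients take cimetidine. Nothing in it shows that cimetidine would carry exposure beyond the range that titration to tolerance already covers. The conclusion needs only the protocol's own description of the interaction and the fact that the drug can be stopped or replaced. It does not depend on how cimetidine is sold, since no list restricts prescription use either.

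**What to change.** Treat cimetidine as erythromycin is treated:

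- add its use to the exclusions in section 4.3 and the synopsis;
- in section 4.4, add cimetidine in any form to the agents barred during screening and throughout the trial, and state its washout (the 6 weeks already used there is the simplest choice);
- in the next paragraph of section 4.4, limit the over-the-counter permission to products other than those barred above;
- add it to the section 5.2 stop list and to the screening visit 1 check.

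The existing interview at each visit then covers it. The document history shows the same edit made for erythromycin in the 31 July 2008 version, in the synopsis, 4.3, 4.4 and both 5.2 lists.

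The cost is one drug name in five places, a washout period and a short qualifier to one sentence. No visit or test is added. Some patients will have to switch drug or will fail screening; the protocol gives no basis for saying how many. If an exclusion is thought too strict, the minimum is a line in section 5.7 telling sites to ask about cimetidine and to stop or replace it before dosing, together with the section 4.4 qualifier reworded to except cimetidine by name.
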